5.5.1.3.4. Time to Appearance of Anti-HBe Antibodies

Appearance of anti-HBe antibodies is defined as a baseline anti-HBe antibodies (qualitative) with a “NEGATIVE” result and a post-baseline assessment with “POSITIVE” result.

Time to appearance of anti-HBe antibodies is defined as the time (days) from the date of first study intervention intake to the date of the first occurrence of anti-HBe antibodies appearance + 1. The participants who did not experience emergence of antibodies or who early withdrew from the study before showing emergence of anti-HBe antibodies will be censored at the last anti-HBe antibodies assessment before the date of withdrawal.

Time to appearance of anti-HBe antibodies will be also analyzed considering the participants who were retreated with NA before achieving appearance of anti-HBe antibodies as censored at the date of NA retreatment.

Time to appearance of anti-HBe antibodies will be calculated only for anti-HBe negative participants.

5.5.1.4. Endpoints for Correlation

5.5.1.4.1. Association Between Baseline Characteristics/Viral Blood Markers and Selected Efficacy Variables

Correlations between baseline characteristics and on-treatment HBV blood markers with off-treatment endpoints will be evaluated. The list of HBV blood markers, including but not limited to, are defined in [Table 6](#).

A categorical off-treatment HBV marker will be evaluated if there is at least 10% response.

Table 6: Pairs of off treatment endpoints and baseline characteristics/on treatment HBV markers

Off treatment HBV marker	Baseline Characteristics/On treatment HBV marker
HBsAg change from baseline at FU Week 24	
 • Age • HBsAg value at baseline • HBsAg change from baseline at Week 12 • HBsAg change from baseline at Week 24 • NA treatment completion at Week 24 (Yes; No) • Treatment failure (Yes; No)
HBsAg change from baseline at FU Week 48	
 • Age • HBsAg value at baseline • HBsAg change from baseline at Week 12 • HBsAg change from baseline at Week 24 • NA treatment completion at Week 24 (Yes; No) • Treatment failure (Yes; No)
HBsAg seroclearance at FU Week 24 (Yes; No)	
 • Age • HBsAg value at baseline • HBsAg change from baseline at Week 12 • HBsAg change from baseline at Week 24 • NA treatment completion at Week 24 (Yes; No) • Treatment failure (Yes; No)
HBsAg seroclearance at FU Week 48 (Yes; No)	
 • Age • HBsAg value at baseline • HBsAg change from baseline at Week 12 • HBsAg change from baseline at Week 24 • NA treatment completion at Week 24 (Yes; No) • Treatment failure (Yes; No)
NA re-treatment at FU Week 24 (Yes; No)	
 • Age • HBsAg value at baseline • HBsAg change from baseline at Week 12 • HBsAg change from baseline at Week 24 • Treatment failure (Yes; No)
NA re-treatment at FU Week 48 (Yes; No)	
 • Age • HBsAg value at baseline • HBsAg change from baseline at Week 12 • HBsAg change from baseline at Week 24 • Treatment failure (Yes; No)
Partial cure at FU Week 24 (Yes; No)	
 • Age • HBsAg value at baseline

Table 6: Pairs of off treatment endpoints and baseline characteristics/on treatment HBV markers

Off treatment HBV marker	Baseline Characteristics/On treatment HBV marker
	
 • HBsAg change from baseline at Week 12 • HBsAg change from baseline at Week 24 • Treatment failure (Yes; No)
Partial cure at FU Week 48 (Yes; No)	
 • Age • HBsAg value at baseline • HBsAg change from baseline at Week 12 • HBsAg change from baseline at Week 24 • Treatment failure (Yes; No)
Functional cure at FU Week 24 (Yes; No)	
 • Age • HBsAg value at baseline • HBsAg change from baseline at Week 12 • HBsAg change from baseline at Week 24 • NA treatment completion at Week 24 (Yes; No) • Treatment failure (Yes; No)
Functional cure at FU Week 48 (Yes; No)	
 • Age • HBsAg value at baseline • HBsAg change from baseline at Week 12 • HBsAg change from baseline at Week 24 • NA treatment completion at Week 24 (Yes; No) • Treatment failure (Yes; No)

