1.2. Study Design

This is a Phase 2a, open-label, single-arm, multicenter study to assess efficacy, safety, tolerability and pharmacokinetics of treatment with JNJ-3989, JNJ-6379 (as applicable), NA, and PegIFN- α 2a in virologically suppressed patients with chronic hepatitis B virus infection. Prior to Protocol Amendment 3, the study intervention also included JNJ-6379. Note that as of Protocol Amendment 3, JNJ-6379 has been removed as study intervention and the study will continue with JNJ-3989, NA and PegIFN- α 2a only. Participants had to stop JNJ-6379 treatment immediately after the implementation of Urgent Safety Measure (USM) and approval of the protocol amendment 3.

Approximately 50 virologically suppressed CHB-infected participants, 18-65 years (inclusive) of age, will be enrolled in this study. Approximately 40% HBeAg-positive participants will be enrolled.

[figure not shown]
The study will be conducted in 4 periods:

- Screening period (4 weeks [if necessary, can be extended to a maximum of 8 weeks decided on a case-by-case basis and in agreement with the sponsor]).
- Treatment Period 1 (12 weeks) consisting of combination treatment with JNJ-3989 + NA.
- Treatment Period 2 (12 weeks) adding PegIFN- α 2a to the combination treatment regimen of Treatment Period 1.
- Follow-up (FU) Period (48 weeks).

The total duration of individual participation will be up to 76 weeks (including 4 weeks of screening).

A schematic of the trial prior to Protocol Amendment 3 is presented in [Figure 1](#).

Figure 1: Schematic Overview of the Study – Prior to Protocol Amendment 3

[figure not shown]

ALT: alanine aminotransferase; DNA: deoxyribonucleic acid; EOS: end of study; EOSI: end of study intervention; FU: follow-up; HBeAg: hepatitis B e antigen; HBsAg: hepatitis B surface antigen; HBV: hepatitis B virus; JNJ-3989: JNJ-73763989; JNJ-6379: JNJ-56136379; LLOQ: lower limit of quantification; n: number of participants; NA: nucleos(t)ide analog; PegIFN-α2a: pegylated interferon alpha-2a; ULN: upper limit of normal; Q4W: every 4 weeks; QD: once daily; QW: once weekly.

^a. If NA treatment completion criteria (HBsAg <10 IU/mL, and HBeAg-negative, and HBV DNA <LLOQ, and ALT <3x ULN) have been met at Week 24, NA will be stopped at the next scheduled visit (ie, FU Week 2), otherwise NA treatment will continue during the complete FU period.

A schematic of the trial as of Protocol Amendment 3 is presented in [Figure 2](#).

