5.1.7. Level of Significance

Due to exploratory nature of this study, no formal test will be performed. Only two-sided 90% CIs will be provided with no adjustment for multiplicity.

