5.4.1.1.5. Functional Cure

Functional cure will be evaluated at each of the following time points separately: FU Week 12, 24, 36 and 48. A participant will be defined as having achieved functional cure (FC) if he/she has:

- met the criteria for stopping NA treatment at Week 24, and
- had HBsAg seroclearance at the given week of interest, and
- not required NA re-treatment between FU Week 2 and the given week of interest.

It can be noted that a participant may achieve HBsAg seroclearance prior to the week of interest, but the HBsAg level <LLOQ has to be shown at the given week of interest to be counted as responder.

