5.5.2. Analysis Methods

All exploratory endpoints will be analyzed using the FAS. The analysis may be repeated in the IFN-FAS and modified FAS/IFN-FAS analysis sets if there is a difference of at least 2 participants between analysis sets.

Some analysis will be performed by group, as defined in Section [5.1.10](#).

Summaries and graphs will be provided for each analysis phase, unless specified otherwise.

All exploratory endpoints will be analyzed based on the observed case data. No imputation for missing data will be used.

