5.5.2.4. Endpoints for Correlation

5.5.2.4.1. Association Between Baseline Characteristics/Viral Blood Markers and Selected Efficacy Variables

Correlations will be evaluated graphically using scatter plots, and heat maps displaying such potential associations.

The following correlation coefficients will be calculated by study intervention arm for the different correlation scenarios:

- Pearson's correlation coefficient for two continuous variables.
- Phi correlation coefficient for two binary variables.
- Point biserial correlation coefficient for one binary variable and one continuous variable.

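### SAP Table 6 correlates functional cure with one of its own components, and runs the NA re-treatment and partial-cure rows in participants who mostly could not have the event

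*SAP*

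**What the plan says.** Table 6 (SAP 5.5.1.4.1) pairs off-treatment outcomes with baseline and on-treatment markers.

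- **Functional cure.** "Functional cure at FU Week 24 (Yes; No" and its FU Week 48 counterpart are paired with six variables, one of them NA treatment completion at Week 24. Section 5.4.1.1.5 requires that a functionally cured participant "met the criteria for stopping NA treatment at Week 24, and" has HBsAg seroclearance at the week of interest, and has "not required NA re-treatment between FU Week 2 and the given week of interest".
- **NA re-treatment.** "NA re-treatment at FU Week 24 (Yes; No" and its FU Week 48 counterpart are paired with age, baseline HBsAg, HBsAg change at Weeks 12 and 24, and treatment failure. The partial-cure rows carry the same five. NA completion is not listed in these rows.
- **Method and population.** Section 5.5.2.4.1 names the "Phi correlation coefficient for two binary variables" and a point biserial coefficient for mixed pairs. Section 5.5.2 states: "All exploratory endpoints will be analyzed using the FAS". A categorical outcome is evaluated only if at least 10% of participants have it.
- **Who stops NA.** The completion criteria are HBsAg <10 IU/mL, HBeAg-negative, HBV DNA <LLOQ and ALT <3x ULN (SAP 5.4.1.1.1). Participants who miss them stay on NA throughout follow-up (Protocol 4.1). Partial cure requires that all study interventions were stopped (SAP 5.4.1.1.14).

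**The concern.** These coefficients and heat maps serve the first exploratory objective, which asks which markers go with response at the end of treatment or off treatment. A reader takes zero to mean no association and the sign to mean its direction.

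For functional cure and NA completion, zero cannot occur once there is a cure, because nobody can be cured without having met the criteria.

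For NA re-treatment and partial cure, the FAS pools participants who stopped NA with participants who stayed on it. The second group scores No because it was not at risk, and it is largely the group with higher Week 24 HBsAg. The coefficient then mixes two questions: who was allowed to stop, and who did well after stopping. A deep Week 24 decline could be reported as a marker of relapse when, among those who stopped, it protects.

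**Working it through.** The plan gives no figure for these correlations. Its only sizing figures are the exact 90% intervals, such as 0.376-0.624 (width 0.248) for 25/50. They reproduce, but do not bear on this point.

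**1. Functional cure and NA completion**

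Inputs: N = 50, from "Approximately 50 virologically suppressed CHB-infected participants, 18-65 years (inclusive) of age, will be enrolled in this study". Let K be completers and C cures. The cells are: completer and cured, C; completer and not cured, K-C; non-completer and cured, 0 by definition; non-completer and not cured, N-K.

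phi = C(N-K) / sqrt[K(N-K)C(N-C)] = sqrt[ C(N-K) / (K(N-C)) ]

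Only the two margins enter. How often non-completers clear HBsAg has no influence.

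| Completers K | Cures C | phi |
|---|---|---|
| 10 | 5 | sqrt(200/450) = 0.67 |
| 20 | 5 | sqrt(150/900) = 0.41 |
| 20 | 10 | sqrt(300/800) = 0.61 |
| 30 | 5 | sqrt(100/1350) = 0.27 |
| 40 | 5 | sqrt(50/1800) = 0.17 |

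Over all tables with N = 50 and at least one cure, the minimum is 0.02. Five cures is the 10% threshold (0.10 x 50), so that threshold does not remove the problem. Among completers the predictor is constant and phi is undefined, so the pair has no corrected value.

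**2. NA re-treatment in the FAS: worked example**

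Assumed data, N = 50. Change is value minus baseline, so a larger decline is more negative.

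- 10 stop NA with change -3.0; 3 are re-treated.
- 10 stop NA with change -2.5; 6 are re-treated.
- 30 continue NA with change -1.5; 0 are re-treated.

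FAS: mean change = (-30 - 25 - 45)/50 = -2.0; re-treated 9/50 = 0.18. Cross-product = (3 x -3.0 + 6 x -2.5) - 50 x (-2.0)(0.18) = -24 + 18 = -6. Sums of squares: 10(1.0) + 10(0.25) + 30(0.25) = 20, and 9 - 81/50 = 7.38. r = -6/sqrt(20 x 7.38) = **-0.49**, so a larger decline looks harmful.

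Stoppers only: mean change -2.75; re-treated 9/20 = 0.45. Cross-product = -24 + 24.75 = 0.75. Sums of squares: 20 x 0.0625 = 1.25, and 20 x 0.45 x 0.55 = 4.95. r = 0.75/sqrt(1.25 x 4.95) = **+0.30**, so a larger decline protects.

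**3. How far this depends on the share who stop**

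Simulation, 200,000 draws per scenario. The assumptions are not from the documents: baseline log10 HBsAg normal (3.3, SD 0.6), kept above 2 to match entry at HBsAg >100 IU/mL; change SD 0.6; stop if Week 24 log10 HBsAg <1 and the other criteria are met (90%); re-treatment logistic in change, with a larger decline always protective among stoppers. There are 12 scenarios per row (slopes 0.5 to 4, intercepts -1 to 1).

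| Mean change | Stop NA | r in FAS | r in stoppers | Wrong sign in FAS |
|---|---|---|---|---|
| -1.8 | 24% | -0.392 to -0.095 | 0.094 to 0.588 | 12 of 12 |
| -2.2 | 40% | -0.375 to -0.006 | 0.103 to 0.596 | 12 of 12 |
| -2.6 | 57% | -0.309 to 0.120 | 0.107 to 0.609 | 9 of 12 |
| -3.2 | 77% | -0.143 to 0.329 | 0.116 to 0.626 | 4 of 12 |

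For treatment failure against re-treatment, phi was negative in the FAS in all 48 scenarios (-0.361 to -0.029) and positive among stoppers in all 48 (0.020 to 0.486).

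In 5,000 trials of N = 50 with slope 1 and intercept 0, the wrong sign appeared in 99%, 97% and 86.5% of trials reaching five events, for mean changes -1.8, -2.2 and -2.6. Those trials were 73%, 98% and 100% of all trials.

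**4. Partial cure**

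No size was computed. The argument is structural: the definition requires all interventions to be stopped, so continuers score No as they do for re-treatment.

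**The case against.** The strongest reply is that little hangs on this. The study is exploratory, and SAP 5.1.7 plans no tests: "Only two-sided 90% CIs will be provided with no adjustment for multiplicity". Section 5.4.2.2.1 separately summarises end-of-treatment markers by NA completion status, seroclearance, partial cure and functional cure. The seroclearance rows of Table 6 give a less circular comparison with NA completion, if seroclearance there means only HBsAg <LLOQ. All this stands and limits the weight of the point.

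It could also be said that leaving NA completion out of the re-treatment and partial-cure rows hints at an intended restriction to stoppers. No text says so. Where the SAP wants an at-risk denominator it states one (5.4.2.1.3.2, 5.4.2.1.10, 5.4.2.1.11).

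Several stronger readings are tempting and are not supported:

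- *All these associations are fixed in advance.* Only the functional-cure pair is. The re-treatment coefficient is distorted: in the scenarios above it ran from -0.39 to +0.33, and the sign was often right when about 77% stopped NA.
- *Completion will look like a strong predictor of cure whatever the data.* It is always positive, but 0.17 is not strong.
- *Continuers can never be re-treated.* Protocol 6.6 lets some participants with raised Week 24 ALT complete NA, and Sections 6.6 and 7.1 let early discontinuers stop it.
- *Spurious significance will follow.* No p-values are planned for these coefficients.

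The simulation does not model HBeAg separately, although about 40% of participants are to be HBeAg-positive. Other runs, with re-treatment unrelated to decline among stoppers and 30% of HBeAg-positive participants assumed to lose HBeAg, gave about 7 to 18 stoppers, a mean FAS r of about -0.20 to -0.35, and a re-treatment row meeting the 10% threshold in only 7 to 94% of datasets. The bias remains, but the row may often not be produced.

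**Conclusion.** The point holds in two parts of different strength. The pairing of functional cure with NA completion is uninformative by definition. This needs no assumption beyond reading Table 6's completion variable as meeting the Week 24 criteria in 5.4.1.1.1. The NA re-treatment and partial-cure rows lack an at-risk population. For re-treatment, the FAS coefficients with Week 24 HBsAg change and treatment failure are distorted and can reverse sign, mainly when a minority stop NA; the size rests on the assumed distributions above. For partial cure only the mechanism is shown.

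The functional-cure rows have a milder version of the same problem. HBsAg <10 IU/mL at Week 24 is built into the outcome, so FAS coefficients with Week 24 HBsAg change and treatment failure partly reflect that component.

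Primary and secondary results are untouched. The change is worth making because it is cheap and alters what these exploratory correlations can be taken to show.

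**What to change.** In Table 6 and Section 5.5.2.4.1:

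1. Delete NA treatment completion at Week 24 from the two functional-cure rows.
2. Compute the NA re-treatment and partial-cure rows only in participants who stopped all study interventions including NA. Report that n, and state the minimum number of events needed. The 10% rule needs restating, since 10% of 10 stoppers is one event.
3. For functional cure, also report the HBsAg-based predictors among participants who met the completion criteria, or add a note that the FAS coefficients partly reflect the HBsAg <10 IU/mL component of the outcome.

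The cost is a table edit and a subset flag. The downsides are a smaller n, a restricted range of Week 24 HBsAg among stoppers, and some rows that may not be evaluable. Among stoppers with HBsAg <10 IU/mL, treatment failure (a decline under 2 log10) implies a baseline below 1,000 IU/mL, so that predictor becomes partly a marker of low baseline and should be read that way.

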5.5.1.5. Sustained HBsAg Response

The definitions of sustained HBsAg response are as follows:

- Definition #1:
 - For participants with Follow-up Week 48 data: participants who had a $>1 \log_{10}$ decline from baseline in HBsAg at Follow-up Week 48 and HBsAg $< 1,000$ IU/mL at Follow-up Week 48.
 - For participants without Follow-up Week 48 data: participants who had a $>2 \log_{10}$ decline from baseline in HBsAg at Follow-up Week 24 or a $>1.5 \log_{10}$ decline in HBsAg at Follow-up Week 36 (most recent value used) and had HBsAg $< 1,000$ IU/mL at the last available timepoint.
- Definition #2:
 - For participants with a $>1 \log_{10}$ decline from baseline in HBsAg at the last Follow-up visit: among the 3 most recent visits, the difference between \log_{10} HBsAg at 2 of the 3 last visits and 1 of the 3 last visits is $< 0.2 \log_{10}$ IU/mL and the difference between \log_{10} HBsAg at 3 of the 3 last visits and 1 of the 3 last visits is $< 0.2 \log_{10}$ IU/mL.
- Definition #3:
 - For participants with a $>1 \log_{10}$ decline from baseline in HBsAg at the last Follow-up visit: among the 3 most recent visits, the difference between \log_{10} HBsAg at 2 of the 3 last visits and 1 of the 3 last visits is $< 0.2 \log_{10}$ IU/mL and the difference between \log_{10} HBsAg at 3 of the 3 last visits and 1 of the 3 last visits is $< 0.2 \log_{10}$ IU/mL and had HBsAg $< 1,000$ IU/mL at the last available timepoint.
- Definition #4:

- Three categories regarding the difference between HBsAg level at the last Follow-up timepoint and Week 24 (EOT):
 - $>0.2 \log_{10}$ decrease: Decreasing level
 - $\leq 0.2 \log_{10}$ increase or $\leq 0.2 \log_{10}$ decrease: Stable level
 - $\leq 0.2 \log_{10}$ increase or $\geq 0.2 \log_{10}$ decrease: Stable or Decreasing level
 - $>0.2 \log_{10}$ increase: Increasing level

For all definitions of the sustained HBsAg response, only participants with at least 24 weeks of follow-up data after JNJ-3989 stop will be used for the analysis.

The count and proportion (%) of participants achieving sustained HBsAg response will be summarized.

Spaghetti plots for HBsAg actual values and change from baseline will be presented by study panel over time using color coding by category.

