5.5.2.5. Sustained HBsAg Response

Summary tables with counts and percentages of participants who meet each of the definition will be presented if there is at least 1 participant who meet the criteria.

Spaghetti plots for both absolute values and changes from baseline of HBsAg will be presented over time for each of the definition.

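### Sustained HBsAg response Definition #4 has no baseline-decline condition and names no response category, so participants whose HBsAg never fell may be counted

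*SAP*

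**What the plan says.** SAP 5.5.1.5, added by SAP Amendment 2 to describe off-treatment HBsAg response better, opens with "The definitions of sustained HBsAg response are as follows" and lists #1 to #4.

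- **#1** requires more than a 1 log10 decline from baseline at Follow-up Week 48 and HBsAg below 1,000 IU/mL. Without Week 48 data it requires more than 2 log10 at Follow-up Week 24 or more than 1.5 log10 at Follow-up Week 36, with the same level limit at the last available timepoint.
- **#2 and #3** both begin "For participants with a $>1 \log_{10}$ decline from baseline in HBsAg at the last Follow-up visit" and then require stability over the last three visits. #3 adds the 1,000 IU/mL limit.
- **#4** reads "Three categories regarding the difference between HBsAg level at the last Follow-up timepoint and Week 24 (EOT"), followed by four bullets: a fall of more than 0.2 log10 (*Decreasing*), a change of at most 0.2 either way (*Stable*), a combined category, and a rise of more than 0.2 (*Increasing*). In typesetting code, the combined category is "\leq 0.2 \log_{10}$ increase or $\geq 0.2 \log_{10}$ decrease: Stable or Decreasing level".

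One restriction applies to all four: at least 24 weeks of follow-up data after JNJ-3989 is stopped. SAP 5.5.2 sets the FAS as the analysis set. On reporting, 5.5.1.5 says "The count and proportion (%) of participants achieving sustained HBsAg response will be summarized", and 5.5.2.5 says "Summary tables with counts and percentages of participants who meet each of the definition will be presented" if at least one participant qualifies.

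**The concern.** A sustained response presupposes a response. Definitions #1 to #3 build that in and #4 does not. Its only input is the change after Week 24, so a participant in whom HBsAg never moved gets the same label as one who fell by 2.5 log10 and stayed there.

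The flat profile can occur under this protocol. Participants enter on stable NA with HBsAg above 100 IU/mL (Protocol 5.1), and NA is stopped only if HBsAg is below 10 IU/mL at Week 24, among other criteria (Protocol 6.6). A participant with no decline therefore continues NA through follow-up.

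The SAP promises a percentage for each definition without saying which category of #4 qualifies. Read as signed changes, *Decreasing*, *Stable* and *Increasing* cover every possible value. So meeting #4 is either undefined or true of everyone with data until someone picks a category. The study is open-label and the study team sees the interim results (Protocol 9.5), so that choice could be made with the data in view. At stake is a line in a sustained-response table that mixes non-responders with durable responders.

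**Working it through.** The SAP attaches no figure to this endpoint, so there is none to reproduce. The check applies the written rules to constructed profiles.

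**Rule for #4.** Let d = log10 HBsAg at last follow-up minus log10 HBsAg at Week 24. *Decreasing*: d < −0.2. *Stable*: −0.2 ≤ d ≤ 0.2. *Increasing*: d > 0.2. Baseline does not appear.

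**Profiles** (log10 IU/mL). The last three follow-up visits are equal, except in the final row, where they are 1.5, 1.45 and 1.4.

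| Profile | Baseline | Week 24 | Last FU | Decline at last FU | d | #1, #2, #3 | #4 |
|---|---|---|---|---|---|---|---|
| No effect | 4.0 | 4.0 | 4.0 | 0.0 | 0.0 | No | Stable |
| Small fall, held | 4.0 | 3.7 | 3.7 | 0.3 | 0.0 | No | Stable |
| Responder, held | 4.0 | 1.5 | 1.5 | 2.5 | 0.0 | Yes | Stable |
| Responder, rise of 0.5 | 4.0 | 1.5 | 2.0 | 2.0 | +0.5 | Yes | Increasing |
| Responder, rise of 0.3 | 4.0 | 1.0 | 1.3 | 2.7 | +0.3 | Yes | Increasing |
| Responder, further fall of 0.1 | 4.0 | 1.5 | 1.4 | 2.6 | −0.1 | Yes | Stable |

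Rows 1 to 3 carry the point: three different treatment outcomes, one label.

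**How often a flat participant is labelled *Stable*.** The documents give no within-participant SD for a single log10 HBsAg value, so assume σ over a range. With no true change, d ~ N(0, 2σ²). Then P(*Stable*) = 2Φ(0.2/(σ√2)) − 1. Read as a signed change, P(*Stable or Decreasing*) = P(d ≤ 0.2) = Φ(0.2/(σ√2)).

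| σ (assumed) | 0.2/(σ√2) | P(Stable) | P(Stable or Decreasing) |
|---|---|---|---|
| 0.05 | 2.828 | 0.995 | 0.998 |
| 0.10 | 1.414 | 0.843 | 0.921 |
| 0.15 | 0.943 | 0.654 | 0.827 |
| 0.20 | 0.707 | 0.520 | 0.760 |

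**The category list.**

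1. Three categories are announced and four are given.
2. A rise of 0.1 is both *Stable* and *Stable or Decreasing*, so the two overlap, although plots are to be coloured by category.
3. Taken literally, the combined category is a rise of at most 0.2 or a fall of at least 0.2. A fall of 0.1 (last profile) is neither, yet it is *Stable*. The combined category thus leaves out part of one of its components.
4. Counting any fall as a negative rise closes that gap but cannot be applied throughout. *Stable* would then be d ≤ 0.2 or −d ≤ 0.2, which is true for every d.

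**The case against.** The best case for the plan is that #4 is a classification and was never meant as a pass rule. It speaks of categories where #1 to #3 state conditions, and the same section colours plots by category. On that reading nothing is counted as a response, and the label is right for what it measures: a participant whose HBsAg rises by 0.5 log10 after Week 24 is increasing. Net decline from baseline is the business of #1 to #3, so disagreement between them and #4 is expected.

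Much of this stands. A reader might infer that the SAP counts *Stable* as a sustained response and treats *Increasing* as failure. It says neither. Nor is labelling a partial rebound *Increasing* a defect in a trajectory measure.

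Safeguards also exist. The endpoint is exploratory, no formal test is planned (SAP 5.1.7), #1 to #3 are tabulated beside it, change from baseline is plotted for these definitions, and treatment failure is reported separately (SAP 5.4.2.1.5). The protocol's background data show pronounced HBsAg declines on JNJ-3989 (Protocol 2.2.3.1), so a wholly flat cohort is unlikely.

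What does not stand is that the text is therefore adequate. If #4 is only a trajectory, it does not belong in a list of definitions for which a count and percentage are promised. If it is a response definition, it lacks both a response condition and a qualifying category.

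**Conclusion.** The point holds in this form. Definition #4 is offered as a definition of sustained HBsAg response, uses only the change after Week 24, has no baseline-decline condition, and names no category as the response. If *Stable* or *Stable or Decreasing* is counted, which the promised percentage for each definition suggests but the SAP does not state, participants who never responded are included and cannot be told apart from responders who held their decline. The category list is wrong as written in any case.

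The logic needs no assumed numbers. The probabilities (76% to 99.8% for *Stable or Decreasing*, 52% to 99.5% for *Stable*, in participants with no true change) are illustrations under assumed SDs and normal errors. They do not predict the trial's result, which also depends on how many participants fail to respond.

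A stronger reading, that #4 makes the sustained-response analysis worthless, is not supported: #1 to #3 each require a decline and are reported alongside. A #4 percentage alone could not support a statement about durability. This should be corrected; it does not touch the primary endpoint.

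**What to change.** 1. Rename #4 *HBsAg trajectory after EOT* and remove it from the sustained-response count in 5.5.1.5 and 5.5.2.5.
2. Tabulate it by Week 24 response (decline from baseline of at least 2 log10, yes or no). That variable is already derived for the primary endpoint.
3. Use three exclusive categories: a decrease of more than 0.2 log10; a change within ±0.2 log10; an increase of more than 0.2 log10. Report *Stable or Decreasing* as the sum of the first two.
4. If #4 is kept as a response definition, restrict it to participants with the Week 24 response and state which category qualifies.

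Borrowing the entry condition of #2 and #3 (more than 1 log10 below baseline at the last follow-up visit) is a weaker repair. It removes flat participants, but it selects on the outcome. To illustrate, assume rebound in responders is N(0.5, 0.4²). Then P(d ≤ 0.2) = Φ(−0.75) = 0.227. After a 2.0 log10 decline at Week 24, the condition is met if the rebound is below 1.0, with probability Φ(1.25) = 0.894, and the proportion among those eligible becomes 0.227/0.894 = 0.25. After a 1.5 log10 decline the probability is 0.50 and the proportion becomes 0.45. The percentage rises because the largest rebounds have been dropped.

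The cost is SAP wording, one table shell and minor programming. No new data are needed.

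### In sustained-response Definition #4 the combined stable-or-decreasing line leaves out falls strictly between 0 and 0.2 log10, so it is not the sum of its two parts

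*SAP*

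**What the plan says.** SAP Section 5.5.1.5 gives four alternative definitions of sustained HBsAg response. Definition #4 opens with "Three categories regarding the difference between HBsAg level at the last Follow-up timepoint and Week 24 (EOT" and then lists four lines:

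1. Decreasing: a fall of more than 0.2 log10.
2. Stable, worded "\leq 0.2 \log_{10}$ increase or $\leq 0.2 \log_{10}$ decrease: Stable level".
3. The composite, labelled "Stable or Decreasing level" and worded in full "\leq 0.2 \log_{10}$ increase or $\geq 0.2 \log_{10}$ decrease: Stable or Decreasing level".
4. Increasing: a rise of more than 0.2 log10.

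The same section limits all four definitions to participants with at least 24 weeks of follow-up data after JNJ-3989 was stopped, and asks for spaghetti plots colour-coded by category. For the output, Section 5.5.2.5 states: "Summary tables with counts and percentages of participants who meet each of the definition will be presented", provided at least one participant meets the criteria. No other section redefines the composite.

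**The concern.** The name of line 3 says that it joins lines 1 and 2, but its inequality does not do so. Line 2 admits falls of up to 0.2; line 3 admits only falls of 0.2 or more. A participant whose HBsAg fell by 0.1 log10 after Week 24 is Stable, is not in the composite, and is not Increasing either.

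Since counts and percentages are planned for the definition, this rule will be programmed. A programmer who follows it literally produces a combined figure that does not equal the sum of its named parts. The error has one direction: it can only remove participants from the composite.

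**Working it through.** **Inputs.** The four lines of Definition #4 in SAP 5.5.1.5. Let d = log10 HBsAg at the last follow-up timepoint minus log10 HBsAg at Week 24. The plan gives no numerical result to reproduce, so the check is of the rules themselves.

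**Step 1: read rise and fall as magnitudes, with no change counted as Stable.**

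| Line | Range of d |
|---|---|
| Decreasing | d < -0.2 |
| Stable | -0.2 <= d <= 0.2 |
| Increasing | d > 0.2 |
| Composite, as written | 0 <= d <= 0.2, or d <= -0.2 |
| Decreasing plus Stable | d <= 0.2 |

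Evaluated from -1.00 to +1.00 in steps of 0.01 (201 points), each value falls in exactly one of Decreasing, Stable and Increasing: 80 + 41 + 80 = 201. The composite misses the 19 points from -0.19 to -0.01, all of them Stable. A fall of exactly 0.2 is in both Stable and the composite, so the gap is the open interval.

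**Step 2: try a signed reading.** If a rise of at most 0.2 means d <= 0.2 whatever the sign, the composite becomes d <= 0.2 and the gap closes. The same convention turns the Stable line into d <= 0.2 or d >= -0.2, which every value satisfies (201 of 201 points). No single reading makes both lines right.

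**Step 3: the size of the error.** Let
- a = number with a fall strictly between 0 and 0.2,
- b = number with d from 0 to 0.2, or a fall of exactly 0.2,
- c = number with a fall above 0.2.

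Then Stable = a + b, Decreasing = c, composite as written = b + c, and the correct composite = a + b + c.
- Shortfall = (a + b + c) - (b + c) = a.
- The composite is below Stable alone when b + c < a + b, that is, when c < a.

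**Step 4: two invented groups of 40, to show the mechanics only.**

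| d = -0.1 (a) | d = +0.1 (b) | d = -0.5 (c) | d = +0.5 | Stable | Decreasing | Composite as written | Correct |
|---|---|---|---|---|---|---|---|
| 20 | 10 | 5 | 5 | 30 | 5 | 15 | 35 |
| 5 | 10 | 20 | 5 | 15 | 20 | 30 | 35 |

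In the first group the composite (15) is half of Stable (30). In the second it is 5 too low but above both of its parts, so nothing about it alone looks wrong.

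**Step 5: range.** The shortfall in the proportion is a/N, where N is the number analysed. It runs from zero, if nobody is in the band, up to the whole analysed group. With N = 50, about the planned enrolment, each participant in the band costs 1/50 = 2 percentage points. The documents give no distribution of d from which to narrow this.

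**The case against.** The intended meaning is hardly in doubt. The label names both parts, each is defined in the same list, and a careful programmer would take d <= 0.2. Where Stable and Decreasing are tabulated, their sum gives the right figure. The endpoint is one of four alternative definitions of an exploratory outcome, in a study with no formal hypothesis (SAP Section 2) and no formal test (SAP 5.1.7). All of this stands, and it sets the weight of the point.

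It is less true that the error would reveal itself. A composite below Stable would be noticed, but that happens only when c < a. Otherwise, as in the second invented group, a reader must add two rows to find the discrepancy.

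A misread sign in the PDF text cannot be excluded, but no comparison sign at that place repairs the line. A strict or non-strict greater-than sign leaves the gap open. A less-than sign repeats the Stable line, or nearly so, and drops the larger falls.

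A reader might infer more than the text supports:
- **That all four categories overlap.** They do not. Decreasing, Stable and Increasing are mutually exclusive; only the composite overlaps its own parts. The lead-in's count of three fits the exclusive classes and is loose only because a fourth line follows. Colour coding works with those three.
- **That the combined count is bound to be impossible.** It falls below Stable only when small falls outnumber falls above 0.2.
- **That the study would understate off-treatment HBsAg control.** The Stable and Decreasing rules are right, so that information is not lost. Only the composite row would be too low.

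**Conclusion.** The composite line is wrong as written. It omits falls strictly between 0 and 0.2 log10 that the plan itself classes as Stable, and undercounts by exactly the number of participants in that band. This rests on reading rise and fall as magnitudes, the only reading under which the Stable line has any content.

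The number of participants affected cannot be derived from the documents; the groups of 40 above are illustrations, not estimates. The consequence is small. Decreasing, Stable and Increasing need no change, the primary endpoint in SAP 5.3 does not use Definition #4, and no inference depends on it. It is a drafting error worth correcting before programming, and no evidence of bias in the study's efficacy conclusions.

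**What to change.** Replace the four lines with rules on one signed change, d = log10 HBsAg at the last follow-up timepoint minus log10 HBsAg at Week 24:

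- Decreasing: d < -0.2
- Stable: -0.2 <= d <= 0.2
- Increasing: d > 0.2
- Derived composite, Stable or Decreasing: d <= 0.2, reported as the sum of Decreasing and Stable

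Reword the lead-in to announce three exclusive categories and one derived composite, and base the plot colours on the three. All existing cut-offs are kept and no new data are needed. The cost is a short edit to SAP 5.5.1.5. If programming is already done, it also takes a check that the composite row equals the sum of its parts.
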